3.6.1. Adverse Events

An AE is considered treatment-emergent adverse event (TEAE) to a given treatment (for a participant who received at least one dose) if the event start date is on or after the treatment period start date and before end of study.

Safety endpoints will be assessed by the spontaneous reporting of:

- Incidence of TEAEs;
- Incidence of serious adverse events (SAEs);
- Incidence of AEs leading to discontinuation.

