9.3. Populations for Analyses

For purposes of analysis, the following populations are defined:

Population	Description
Enrolled	All participants who sign the ICF.
Evaluable – Open Label (Evaluable-OL)	All participants receiving at least 1 dose of study intervention in the open-label run-in period
Evaluable – Double-Blind (Evaluable-DB)	All randomized participants receiving at least 1 dose of study intervention in the double-blind maintenance period. Participants will be analyzed according to the intervention they are randomized to.
Safety – Double-Blind (Safety-DB)	All participants randomly assigned to study intervention and who take at least 1 dose of study intervention in the double-blind maintenance period. Participants will be analyzed according to the intervention they actually received.
Safety – Double-Blind Maintenance Period (excluding data from flare treatment period) (Safety-QD)	All participants randomly assigned to study intervention and who take at least 1 dose of study intervention in the double-blind maintenance period (excluding data from the flare treatment period). Participants will be analyzed according to the intervention they actually received. Safety data from flare treatment periods will be summarized separately.
Safety – flare treatment period (Safety-flare)	All participants who receive at least 1 dose of study intervention in the flare treatment period during the double-blind maintenance period. Participants will be analyzed according to the intervention they received in QD period.

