9.4.2. Safety Analyses

All safety analyses will be performed on the Safety Population.

Endpoint	Statistical Analysis Methods
Primary	
AEs, SAEs, local tolerability, discontinuations, and clinically significant changes in vital signs will be descriptively summarized and will be presented in tabular and/or graphical format by open-label run-in period, flare treatment period in the maintenance period, and QD period. No imputation will be made for missing safety data.

CCI

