4. ANALYSIS SETS (POPULATIONS FOR ANALYSIS)

For purposes of analysis, the following populations are defined:

Population	Description
Enrolled	All participants who sign the informed consent form.
Evaluable-OL (Eval-OL)	All participants receiving at least 1 dose of study intervention in the OL period
Safety-OL (SAF-OL)	All participants receiving at least 1 dose of study intervention in the OL period. It is same as Evaluable-OL
Evaluable-DB (Eval-DB)	All randomized participants with success in ISGA and EASI50 criteria as responders at randomization and receiving at least 1 dose of study intervention in the DB period. Participants will be analyzed according to the intervention they are randomized to.
Safety-DB (SAF-DB)	All randomized participants receiving at least 1 dose of study intervention in the DB period. Participants will be analyzed according to the intervention they actually received.
Safety (SAF)	All participants receiving at least 1 dose of study intervention during the study.

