6.7.1. Adverse Events

The safety data will be summarized separately by period: OL period for SAF-OL, DB QD period for SAF-DB, and flare treatment period for SAF-DB in accordance with Pfizer Data Standards. All safety data will be summarized descriptively through appropriate data tabulations, descriptive statistics, categorical summaries, and graphical presentations. The safety data will be summarized for overall events and treatment area events. Safety endpoints for the study include:

- Incidence of TEAEs.
- Incidence of SAEs and AEs leading to discontinuation.

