Appendix 2: Definition and Use of Visit Windows in Reporting

Below visit windows will be used for ISGA, EASI, and %BSA during OL period.

OL Visit Label	Target Day	Definition [Day window]
Screening		Days -28 to -1
OL Weeks 0-8	Days of OL Period	
OL_Day 1/Week 0	Day 1, Baseline	Day 1
OL_Week 2	15	Days 2 to 22
OL_Week 4	29	Days 23 to 36
OL_Week 6	43	Days 37 to 50
OL_Week 8	57	Day 51 to end of OL
End of OL		OL discontinuation or double-blind randomization. IF participants don't enter maintenance period, the follow up period is included in OL.

Below visit windows will be used for Dermatology Quality of Life Assessments and POEM during OL period.

OL Visit Label	Target Day	Definition [Day window]
Screening		Days -28 to -1
OL Weeks 0-8	Days of OL Period	
OL_Day 1/Week 0	Day 1, Baseline	Day 1
OL_Week 1	8	Days 2 to 11
OL_Week 2	15	Days 12 to 18
OL_Week 3	22	Days 19 to 25
OL_Week 4	29	Days 26 to 32
OL_Week 5	36	Days 33 to 39
OL_Week 6	43	Days 40 to 46
OL_Week 7	50	Days 47 to 53
OL_Week 8	57	Day 54 to end of OL
End of OL		OL discontinuation or double-blind randomization. IF participants don't enter maintenance period, the follow up period is included in OL.

Below visit windows will be used for efficacy variables during DB period.

	Target Day	Definition [Day window]
DB Weeks 0-52	Days of DB Period	
DB Day 1/Week 0	1	Day 1
DB_Week 4	29	Days 2 to 43
DB_Week 8	57	Days 44 to 71
DB_Week 12	85	Days 72 to 99
DB_Week 16	113	Days 100 to 127
DB_Week 20	141	Days 128 to 155
DB_Week 24	169	Days 156 to 183
DB_Week 28	197	Days 184 to 211
DB_Week 32	225	Days 212 to 239
DB_Week 36	253	Days 240 to 267
DB_Week 40	281	Days 268 to 295
DB_Week 44	309	Days 296 to 323
DB_Week 48	337	Days 324 to 351
DB_Week 52	365	Days 352 to last available data

Note: Participants will have an end-of-study (follow-up) by phone at least 28 days after the last study dose of any period.

For the time points just prior and after initiation of a new episode, the initiation date of the episode is the cutoff date for the visit windows.

Below visit windows will be used for efficacy variables during first flare period.

	Target Day	Definition [Day window]
First Flare Weeks	Days of First Flare Period	
First Flare Day 1/Week 0	1	First Day of first flare period
First Flare_Week 4	29	Days 2 to 43
First Flare_Week 8	57	Days 44 to 71
First Flare_Week 12	85	Days 72 to end of first flare period or end of DB period

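### The SAP's treatment-emergent window has no end at the next treatment switch, which does not fit the by-period adverse event tables, and the flare-period table names SAF-DB where the protocol defined Safety-flare.

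*SAP*

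**What the plan says.** SAP 3.6.1 makes an event treatment-emergent to a given treatment, for a participant who had at least one dose, "if the event start date is on or after the treatment period start date and before end of study". The start is tied to the treatment period; the end is not.

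SAP 6.7.1 asks for separate adverse event summaries by period: "OL period for SAF-OL, DB QD period for SAF-DB, and flare treatment period for SAF-DB". Protocol 9.4.2 has the same layout: "by open-label run-in period, flare treatment period in the maintenance period, and QD period". In Protocol 9.3, the Safety-QD definition leaves flare-period data out and says they are summarised separately.

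For the flare period, Protocol 9.3 defines Safety-flare: "All participants who receive at least 1 dose of study intervention in the flare treatment period during the double-blind maintenance period". It adds a display rule: "Participants will be analyzed according to the intervention they received in QD period". SAP section 4 has no Safety-flare set. SAF-DB, which SAP 6.7.1 names for the flare table, is "All randomized participants receiving at least 1 dose of study intervention in the DB period", whether or not the participant ever had flare treatment.

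SAP Appendix 2 does bound periods in its visit-window tables. The open-label period ends at "OL discontinuation or double-blind randomization", and around a new episode "the initiation date of the episode is the cutoff date for the visit windows". For safety, the appendix says only that the sponsor's standards will be followed.

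**The concern.** Treatments follow one another within a participant: open-label BID for up to 8 weeks, blinded QD, open-label BID for each flare (up to 12 weeks, Protocol 4.1), then blinded QD again. A window that closes only at end of study overlaps every later treatment, whereas tables by period need each event placed in one period. No text in either document says how that is done.

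The flare table raises a separate question. Its events can come only from participants who had flare treatment, but the population named for it is everyone dosed in the double-blind period. If that population supplies the percentage denominator, incidence is diluted, and unequally by arm when the arms flare at different rates.

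Incidence of treatment-emergent adverse events is the primary safety endpoint, and these tables carry the long-term safety evidence for QD use.

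**Working it through.** **Step 1: the window against the tables.** Take a vehicle participant with an event that starts during open-label flare BID.

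| Rule | Where the event counts |
|---|---|
| SAP 3.6.1 read literally | run-in BID, vehicle QD and flare BID, since it starts after all three period starts and before end of study |
| SAP 6.7.1 and Protocol 9.4.2, by period of onset | flare period only |

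Both rules cannot hold for the same table, so there are two cases.

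**Case (a): SAP 3.6.1 governs.** Flare-BID events enter the QD columns, including vehicle, and double-blind events enter the run-in column. The flare numerator also takes in events that start after flare treatment has ended, so the dilution factors in Step 2 do not apply. The documents give no adverse event rates for QD maintenance, so the effect cannot be sized from them.

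**Case (b): the by-period layout governs.** The contamination largely disappears and the denominator question remains. It is sized below.

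**Step 2: flare-table denominator in case (b).** Inputs from Protocol 9.2: 162 first flares, about 250 randomised 1:1, hazard ratio 0.556 (a 1.8 ratio of medians).

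Check of the inputs first. Schoenfeld power is Φ(√162/2 × |ln 0.556| − 1.96) = Φ(3.736 − 1.960) = Φ(1.776) = 96.2%, against the stated 96%. The planning figures reproduce.

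If the numerator is confined to the flare period and the denominator is all of SAF-DB, true incidence among flare-treated participants is multiplied by the share who flare. This assumes that everyone with a first flare is dosed in a flare period.

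- Overall: 162/250 = 0.648.
- By arm: solve (n/2)(pv + pc) = 162 with pc = 1 − (1 − pv)^(1/1.8), where pv and pc are the shares flaring on vehicle and crisaborole (exponential times, no dropout).

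| Randomised n (200 and 300 are assumed) | Overall | Vehicle pv | Crisaborole pc | pv/pc |
|---|---|---|---|---|
| 200 | 0.810 | 0.899 | 0.721 | 1.25 |
| 250 | 0.648 | 0.754 | 0.542 | 1.39 |
| 300 | 0.540 | 0.644 | 0.436 | 1.48 |

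For example, a true 10% incidence among flare-treated participants in both arms would show at n = 250 as 6.5% overall, and as 7.5% for vehicle against 5.4% for crisaborole.

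Sensitivity: with exponential dropout of 10% to 30% at n = 250 and events held at 162, the shares are 0.751 to 0.743 for vehicle and 0.545 to 0.553 for crisaborole, and the ratio is 1.38 to 1.34. At a hazard ratio of 1 the two factors are equal and the ratio is 1.

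**The case against.** The best defence is to read the sections together. SAP 3.6.1 defines treatment emergence; SAP 6.7.1 specifies the tables, and says by period. Protocol 9.3 keeps flare data out of the QD summary. On that reading a programmer assigns events by period of onset, and what is missing is one sentence and a switch-day convention. The sponsor's standards, to which the SAP defers, may already contain both. This carries weight: it makes case (b) the more natural reading. It does not correct 3.6.1, which still states a different rule, and the standards are not in the documents.

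On the population, Protocol 9.4 lets the SAP modify the protocol, the SAP history records that population definitions were changed, and Protocol 9.4.2 itself refers only to the Safety Population. SAP 6.7.1 does not state a percentage denominator, and the example first-flare shell in SAP Appendix 3 counts only participants in the flare period (N = 13, against 138 in the same arm at double-blind Day 1; example figures for efficacy data). So the departure is permitted and the dilution is conditional. But the history shown gives no specific reason for dropping Safety-flare, and the only population named for the flare table is SAF-DB. The at-least-one-dose clause in 3.6.1 limits who can have a treatment-emergent event; it does not set a denominator.

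It is also fair that the 1.39 ratio compares arms while both receive the same open-label BID. It is not the randomised safety contrast.

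**Conclusion.** Two faults stand. The window in SAP 3.6.1 has no end at the next treatment switch and is inconsistent with the by-period summaries. SAP 6.7.1 names SAF-DB for the flare table where the protocol defined Safety-flare. Under case (b), with all of SAF-DB as denominator, the dilution is about 0.65 overall and 0.75 against 0.54 by arm, an artificial ratio of about 1.39 (1.25 to 1.48 for 200 to 300 randomised). These rest on planning figures, exponential flare times and no dropout. Case (a) cannot be sized.

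A reader might infer more, and the documents do not support it:

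- That contaminated QD columns and a diluted flare table occur together. They arise from opposite readings; the dilution factors need the numerator confined to the flare period.
- That the run-in table would cover 64 weeks (8 + 52 + 4), or 68 with the one 4-week flare course allowed past Week 52. That is a worst-case literal reading. The by-period wording and the open-label end in SAP Appendix 2 point the other way.
- That the application site pain rates in Protocol 2.3 (4.4% and 1.2%) size the contamination. They come from the BID studies and are not QD-maintenance rates.
- That omitting Safety-QD is a fault too. The QD-period table on SAF-DB has the same people and the same data restriction.

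Safety is descriptive, so no test or decision rule is affected. Severity is minor to should-fix.

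**What to change.** In SAP 3.6.1, for the period tables, assign each event to the treatment period (run-in, QD or flare) in which it starts: from the first dose of that period to before the first dose of the next. Let the last period run to the end of the collection period in Protocol 8.3.1, at least 28 days after last dose. State how an event dated on a switch day is placed. If the sponsor's standards already hold this rule, write it into 3.6.1.

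In SAP section 4 and 6.7.1, restore Safety-flare as population and percentage denominator for the flare-period tables, shown by the intervention received in the QD period.

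The cost is SAP wording and one derivation flag built from dose dates by treatment period. No new data are needed.

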3.6.2. Laboratory Data

Laboratory testing will be performed at screening and post baseline only if clinically indicated. Below are the protocol-required safety laboratory assessments:

Laboratory Assessments	Parameters	
Hematology	Platelet Count Red blood cell (RBC) Count Hemoglobin Hematocrit	White blood cell (WBC) count (% and absolute): Neutrophils Lymphocytes Monocytes Eosinophils Basophils
Clinical Chemistry	Albumin Alanine Aminotransferase (ALT) Aspartate Aminotransferase (AST) Sodium Glucose (non-fasting)	Blood urea nitrogen (BUN) Potassium Alkaline phosphatase Total bilirubin Total Protein Calcium Creatinine Chloride Bicarbonate or total CO ₂
Urine Pregnancy	For all WOCBP: Test kit (dipsticks) provided by the central laboratory. The results of the urine dipstick test must be recorded in the source document and made available for study review.	
Other Tests	Follicle-stimulating hormone (only for post-menopausal status confirmation at screening). Serum beta human chorionic gonadotropin (β-hCG) pregnancy test (for all WOCBP at screening, and for pregnancy status confirmation if urine dipstick pregnancy test is positive or if a urine dipstick test cannot be confirmed as negative [eg, an ambiguous result]).	

3.6.3. Vital Signs

Temperature and pulse rate will be assessed.

3.6.4. Physical Examinations

A complete physical examination will include, at a minimum, assessments of general appearance, skin, head, ears, eyes, nose, throat, mouth, skin, heart, lung, breast, lymph nodes, extremities, abdomen, external genitalia (optional), and neurological function. In addition, an assessment will be made for skin abnormalities other than AD, including scalp.

A targeted physical examination will include, at a minimum, assessments of the skin, heart, lungs, and abdomen and examination of body systems where there are symptom complaints by the participant.

Height and weight will also be measured and recorded.

4. ANALYSIS SETS (POPULATIONS FOR ANALYSIS)

For purposes of analysis, the following populations are defined:

Population	Description
Enrolled	All participants who sign the informed consent form.
Evaluable-OL (Eval-OL)	All participants receiving at least 1 dose of study intervention in the OL period
Safety-OL (SAF-OL)	All participants receiving at least 1 dose of study intervention in the OL period. It is same as Evaluable-OL
Evaluable-DB (Eval-DB)	All randomized participants with success in ISGA and EASI50 criteria as responders at randomization and receiving at least 1 dose of study intervention in the DB period. Participants will be analyzed according to the intervention they are randomized to.
Safety-DB (SAF-DB)	All randomized participants receiving at least 1 dose of study intervention in the DB period. Participants will be analyzed according to the intervention they actually received.
Safety (SAF)	All participants receiving at least 1 dose of study intervention during the study.

5. GENERAL METHODOLOGY AND CONVENTIONS

Final analyses will occur after database release.

5.1. Hypotheses and Decision Rules

The primary objective is to establish the superiority of a crisaborole QD to a vehicle QD; detecting a 1.8 ratio of median time of being flare-free (hazard ratio of 0.556) in the first flare-free period at a significance level of 0.05 (2-sided, log-rank test).

5.1.1. Statistical Decision Rules for Multiple Comparisons

A step-down closed testing procedure and Bonferroni's method will be used for Type I error control for testing the primary endpoint and the key secondary endpoints. The order of testing is as follows:

1. Flare-free maintenance up until the onset of the first flare during the DB period.
2. Number of flare-free days over 52 weeks.
3. Number of flares over 52 weeks.

4. Pruritus response maintenance up until the onset of the first flare (ISGA ≥ 2), defined as the maintenance of improvement $\geq 50\%$ (ie, if 50% or more of the improvement in pruritus from the baseline to the randomization is maintained). Analysis will be performed for 5 responder subgroups:
 - ≥ 12 years of age with OL baseline Peak Pruritus NRS ≥ 3 and ≥ 3 points reduction OL baseline to randomization in Peak Pruritus NRS.
 - ≥ 12 years of age with OL baseline Peak Pruritus NRS ≥ 4 and ≥ 4 points reduction OL baseline to randomization in Peak Pruritus NRS.
 - 6- <12 years of age with OL baseline PRIS Scale ≥ 2 and ≥ 2 points reduction OL baseline to randomization in PRIS Scale.
 - 3 months- <6 years of age with OL baseline ORIS Scale ≥ 3 and ≥ 3 points reduction OL baseline to randomization in ORIS Scale.
 - 3 months- <6 years of age with OL baseline ORIS Scale ≥ 4 and ≥ 4 points reduction OL baseline to randomization in ORIS Scale.

The statistical significance can be claimed for a given endpoint in the sequence only if the prior endpoint in the sequence is significant. For the endpoints of 1-3, the significance level is 0.05. For pruritus response maintenance, Bonferroni's method is used to adjust the significance level. The significance level is 0.01 for each subgroup, there is no testing order. Only the subgroup with p-value ≤ 0.01 can claim significance after the primary endpoint and other two secondary endpoints are statistically significant.

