9.2. Sample Size Determination

A total of 162 events will provide approximately 96% power to detect a 1.8 ratio of median time of being flare-free (hazard ratio of 0.556) in the first QD period between crisaborole and vehicle at a significance level of 0.05 (2-sided, log-rank test). To get 162 events (first flare), approximately 250 participants who are eligible responders will be randomized (ratio=1:1) into the double-blind maintenance period of the study. When 162 events are observed, the randomization will be stopped even if less than 250 participants are randomized. On the other hand, if 250 participants are randomized, but 162 events cannot be reached, more participants will be randomized.

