6.2.3. Maintenance of Pruritus Response until Onset of First Flare (ISGA ≥ 2)

The third key secondary endpoint is duration of maintenance of pruritus response. It is the time from randomization to the loss of pruritus response or first flare onset (ISGA ≥ 2) during the 52-week DB period for participants who are pruritus responders at randomization. Pruritus response is maintained if $\geq 50\%$ of pruritus reduction from OL baseline to randomization is not lost.

- Estimand strategy: Hypothetical ([Section 2.1.2.3](#)).
- Analysis Population: Evaluable-DB.
- Analysis method: Time-to-event analysis, Kaplan-Meier (product limit) method and log-rank test ([Section 5.2.4](#)).
- Intercurrent events: intercurrent events include discontinuation of treatment, first flare [ISGA ≥ 2]. If an event (eg, death, first flare [ISGA ≥ 2], lost to follow up, or end of study) occurs before loss of pruritus response for the first flare-free period, the duration of maintenance of pruritus response is the time from randomization to the first intercurrent event and is censored. When loss of pruritus response occurs first, the duration of maintenance of pruritus response is not censored.

- Reporting results: At each month, the proportion of participants who maintained pruritus response in the first flare-free period, time-to-event curve, median (95% CI) time of maintaining pruritus response, and number (%) of censored participants for each treatment group, and p-value from log-rank test will be presented.

The analysis will be performed separately for each age and pruritus response subgroups:

- ≥ 12 years of age with OL baseline Peak Pruritus NRS ≥ 3 and ≥ 3 points reduction from OL baseline to randomization in Peak Pruritus NRS.
- ≥ 12 years of age with OL baseline Peak Pruritus NRS ≥ 4 and ≥ 4 points reduction from OL baseline to randomization in Peak Pruritus NRS.
- 6- <12 years of age with OL baseline PRIS Scale ≥ 2 and ≥ 2 points reduction from OL baseline to randomization in PRIS Scale.
- 3 months- <6 years of age with OL baseline ORIS Scale ≥ 3 and ≥ 3 points reduction from OL baseline to randomization in ORIS Scale.
- 3 months- <6 years of age with OL baseline ORIS Scale ≥ 4 and ≥ 4 points reduction from OL baseline to randomization in ORIS Scale.

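### The five pruritus tests use plain Bonferroni at 0.01 each, which is valid; Holm's step-down keeps the same 0.05 familywise control and never rejects fewer, for a modest gain in power

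*SAP*

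**What the plan says.** SAP 5.1.1 sets a fixed sequence: time to first flare, number of flare-free days, number of flares, then maintenance of pruritus response. On the first three it says "For the endpoints of 1-3, the significance level is 0.05". SAP 5.1 gives the sidedness for the primary test: "at a significance level of 0.05 (2-sided, log-rank test").

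On the fourth it says "Analysis will be performed for 5 responder subgroups". These are at least 12 years with a cut-off of 3 points or of 4 points, 6 to under 12 years with a cut-off of 2 points, and 3 months to under 6 years with a cut-off of 3 points or of 4 points. The multiplicity rule is "For pruritus response maintenance, Bonferroni's method is used to adjust the significance level", followed by "The significance level is 0.01 for each subgroup, there is no testing order". A closing sentence sets a p-value cut-off of 0.01 and adds the gate: a subgroup "can claim significance after the primary endpoint and other two secondary endpoints are statistically significant".

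Protocol 9.4.1.1 has the same rule. Nothing follows pruritus in the hierarchy. SAP 6.2.3 gives the test for each subgroup: "Analysis method: Time-to-event analysis, Kaplan-Meier (product limit) method and log-rank test".

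**The concern.** Each pruritus test stays at 0.01 whatever happens to the other four. When one hypothesis is rejected, its share of alpha is not passed on. The opening sentence of SAP 5.1.1 names a step-down closed procedure, but the rules that follow apply it to the sequence of endpoints. Within the pruritus family nothing steps down.

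Holm's procedure reuses that alpha with the same guarantee, and three features of the plan make it easy to adopt:

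- The observed p-values set Holm's order, so the absence of a prespecified testing order is respected.
- The family is last in the hierarchy, so no alpha has to be kept for later tests.
- Plain Bonferroni gives simpler simultaneous confidence intervals, but SAP 6.2.3 plans no multiplicity-adjusted interval for the treatment effect.

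At stake is power for second and later claims in the last alpha-controlled key secondary family. That family already splits the roughly 250 randomised participants by age and then by pruritus response.

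**Working it through.** **Inputs from the documents.** Family alpha 0.05, five hypotheses, 0.01 per test (SAP 5.1.1); two-sided testing, stated for the primary log-rank test and assumed for pruritus (SAP 5.1); hazard ratio 0.556, 162 events, 1:1 allocation and about 250 randomised, all for the primary endpoint (Protocol 9.2).

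**Inputs not in the documents.** Pruritus events, effects and correlations. Every power figure for pruritus below is therefore an assumption.

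**1. The plan's own figures.** Bonferroni: 0.05/5 = 0.01, as stated. For the primary endpoint, "A total of 162 events will provide approximately 96% power to detect a 1.8 ratio" in median flare-free time. By Schoenfeld's formula the mean z is √(162/4) × |ln 0.556| = 6.364 × 0.587 = 3.74, and power is Φ(3.74 − 1.96) = 0.962, which agrees with 96%.

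**2. Holm thresholds.** For ordered p-values, 0.05/(5 − i) with i = 0 to 4 gives 0.0100, 0.0125, 0.0167, 0.0250 and 0.0500, stopping at the first failure. None is below 0.01, so every Bonferroni rejection is also a Holm rejection. For illustration, p = 0.004, 0.011, 0.015, 0.020 and 0.040 give one claim under the plan's rule and five under Holm.

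**3. Familywise error** (1,000,000 simulated trials per scenario; correlation only within the two pairs of nested subgroups).

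| Scenario | Bonferroni | Holm |
|---|---|---|
| All five nulls true, correlation 0 / 0.7 / 0.9 | 0.049 / 0.045 / 0.039 | the same |
| Three real effects (mean z 3.5, 3.5, 3.0), two nulls, same correlations | 0.020 / 0.018 / 0.015 | 0.041 / 0.036 / 0.031 |

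Holm uses more of the permitted error in the second case and stays within 0.05.

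**4. Power at assumed event counts** (hazard ratio 0.556 in every subgroup, correlation 0.9 within nested pairs, 1,000,000 trials).

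| Events per subgroup | Power per test, Bonferroni | Power per test, Holm | Expected claims | At least one claim (both rules) |
|---|---|---|---|---|
| 16–20 | 8–10% | 9–11% | 0.47 v 0.52 | 0.31 |
| 28–40 | 15–24% | 18–26% | 0.93 v 1.07 | 0.52 |
| 40–60 | 24–38% | 29–42% | 1.46 v 1.71 | 0.70 |

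The gain is about 1 to 6 points per test. In no simulated trial did Bonferroni reject a hypothesis that Holm did not.

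**5. Power by mean z** (same mean z in all five tests, correlation 0.85 within nested pairs, 400,000 trials). Bonferroni power per test is Φ(z − 2.576). The events needed at hazard ratio 0.556 are 4z²/(ln 0.556)², where (ln 0.556)² = 0.3446.

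| Mean z | Events per subgroup | Bonferroni | Holm |
|---|---|---|---|
| 1.5 | 26 | 14% | 16% |
| 2.0 | 46 | 28% | 33% |
| 2.5 | 73 | 47% | 56% |
| 3.0 | 104 | 66% | 77% |

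**6. Are the last two rows plausible?** The three age bands do not overlap, so mean z of 2.5 needs at least 3 × 72.6 ≈ 218 loss-of-response events, and mean z of 3.0 needs at least 3 × 104.5 ≈ 313. About 250 participants are to be randomised, only pruritus responders count, and a first flare censors them. At hazard ratio 0.556, 313 events exceed the planned sample and 218 would be about 87% of it.

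**The case against.** The strongest objection is that nothing here is wrong. The two documents agree, 0.05/5 is exact, Type I error is strongly controlled and no analyst could misread the rule. On that view, preferring Holm is a matter of taste. All of this stands except the conclusion. A choice between two valid procedures is more than taste when one rejects everything the other does, carries the same guarantee and gives up nothing that this plan uses.

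The objection to the size stands. A reader might infer a gain of 9 to 11 points per test, or a rise from 23% to about 50% in the chance of claiming all five (mean z of 3.0, nested correlation 0.85). The documents support neither. They give no pruritus inputs, and step 6 shows that such z-values need more events than the trial can plausibly supply at its own design effect.

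A reader might also infer that the loss is greater here because the 4-point groups are nested in the 3-point groups. As a statement about power per test, that is not supported. At mean z of 2.5 the gain is about 9 points with or without the correlation. At 3.0 it is slightly smaller with nesting (11 v 12 points), and at 1.5 nesting adds less than one point.

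Two limits also stand. Holm's first threshold is 0.01, so the chance of any pruritus claim is unchanged. Where a further claim comes from a nested subgroup, it rests largely on the same participants at another cut-off and adds little new information.

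**Conclusion.** The point holds as one of efficiency. The rule in SAP 5.1.1 and Protocol 9.4.1.1 is valid. Holm at an overall 0.05 gives the same strong familywise control under any dependence, including the nested subgroups, and cannot lose a claim that Bonferroni would make. That much follows from the thresholds and needs no assumption about the data.

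The size does need assumptions. With the primary hazard ratio of 0.556 applied to every pruritus subgroup and 16 to 60 events in each, the gain is about 1 to 6 points of power per test. It reaches about 9 to 11 points only at optimistic mean z of 2.5 to 3.0. All of it falls on second and later claims. When some nulls are true, Holm spends more of the permitted error (0.031 to 0.041 against 0.015 to 0.020 in the case simulated) and remains below 0.05. The priority is low.

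**What to change.** Before unblinding, in both SAP 5.1.1 and Protocol 9.4.1.1, replace two sentences: the one that sets 0.01 for each subgroup and the one that limits claims to subgroups with p at or below 0.01. In their place, state that the five pruritus p-values are tested by Holm's step-down at an overall two-sided 0.05. The ordered thresholds are 0.05/5, 0.05/4, 0.05/3, 0.05/2 and 0.05, stopping at the first failure. Keep the condition that endpoints 1 to 3 must all be significant first. Changing only the first sentence would leave the two in conflict.

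No new data, assumptions or sample size are needed. The wording change is small, but the process may not be. Protocol 9.4 calls for an amendment when a key secondary analysis is changed in a major way, and Protocol 10.1.1 requires ethics approval of amendments. The sponsor should decide whether this change counts as major and, if so, could include it in an amendment made for other reasons.
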